5.2 STUDY MATERIALS

5.2.1 LENSES

All study lenses are approved by Health Canada. They will be worn bilaterally, and on a daily disposable basis, therefore no lens care solution is required.

Table 1: Lens characteristics & parameter to be used in the study

	Test lens	Control lens
Manufacturer	CooperVision, Inc.	Alcon
Material	stenfilcon A	verofilcon a
HC licence #	91502	101910

Dk/t (barrer/cm)	100	100
Water content	54%	51%
Sphere power (D)	-2.00 to -5.00 (0.25 steps)	-2.00 to -5.00 (0.25 steps)
Base curve (mm)	8.4	8.3
Diameter	14.2	14.2
Replacement schedule	Daily disposable	Daily disposable

5.2.2 REWETTING DROPS

Participants who habitually use rewetting drops will be asked to refrain during the study, unless necessary for continued lens wear. Participants will keep track of rewetting drop usage, and this will be recorded at each visit. Rewetting drops may be used in the event of any clinical observation and/or adverse event noted during the study.

5.2.3 ORDERING CONSUMABLES

All study lenses (test and control) will be provided by CooperVision.

5.2.4 CONTACT LENS DISPENSING

Lenses will be provided to the participant after being transferred, complete with blister pack solution, to a contact lens cup; this will maintain participant masking and aid investigator masking. The use of saline for rinsing the contact lens prior to insertion is permitted if necessary. Saline will not be dispensed during the study.

5.2.5 CONTACT LENS DISPOSAL

Participants will be instructed to dispose of the worn lenses daily, and return any unworn lenses in their packaging at their next study visit. All contact lenses worn to each 1-week follow up visit will be collected and stored at -80C. These collected lenses will be shipped to CooperVision at the end of the study. The lens deposits will be evaluated and analysed for composition and quantity, no genetic assessments will be conducted.

Additionally, worn lenses associated with adverse events shall be retained at CORE and returned to CooperVision if requested to do so. Typical analysis in these cases relates to inspection for damage and/ or bacterial contamination. No genetic assessments will be conducted.

Upon completion of the study, all non-dispensed and the returned unworn lenses will be destroyed, unless otherwise directed by the study Sponsor.

5.2.6 PRODUCT ACCOUNTABILITY

Accountability logs will be kept to include the number of lenses received, dispensed, unused and, if relevant, returned to sponsor. All products dispensed to each participant will be recorded in the study log.

5.3 SCHEDULED AND UNSCHEDULED VISITS

This study has 5 visits. The visits are as follows:

- **Visit 1:** Screening, baseline assessments, fitting of both study lenses.
- **Visit 2:** Dispense lens type #1 (normally combined with Visit 1)
- **Visit 3:** 1-week follow-up assessment of lens type #1 (6 to 10 days after Visit 2), worn lens collection
- **Visit 4:** Dispense of lens type #2 (normally combined with Visit 3)
- **Visit 5:** 1-week follow-up assessment of lens type #2 and study exit (6 to 10 days after Visit 4), worn lens collection

A scheduled follow-up visit may only take place when the participant attends wearing the study lenses for 6-8 hours. If this is not the case and the participant is not experiencing any problems with the lenses, the appointment will be rescheduled, ideally within the visit window.

Visits that fall outside of the specified visit windows will be designated as protocol deviations and at the end of the study, the data collected during protocol deviations will be assessed for their suitability to be included in the analysis population.

5.3.1 STUDY VISITS

The summary of visit codes is shown in Table 2.

Table 2: Summary of visit codes

Visit #	Day/s	Visit code	Visits	Duration (hours)
Visit 1	0	V1 (V1R1, & V1R2 for re-screening if required)	Screening, baseline & fit of both study lens	1.25
Visit 2	0	V2	Dispense lens type #1	0.75

9. [REDACTED]
[REDACTED]
[REDACTED]
[REDACTED]
[REDACTED]

- a. [REDACTED]
[REDACTED]
[REDACTED]
[REDACTED]
[REDACTED]
[REDACTED]
[REDACTED]
[REDACTED]
[REDACTED]
[REDACTED]

12. The investigator will confirm that the participant meets the eligibility specifications set out in the inclusion criteria and exclusion criteria and is eligible to continue in the study.

13. Trial fitting of both study lenses:

- a. The contact lens power will be chosen based on the vertexed spectacle refraction. For each eye, the test and control lenses will be optimized for vision, with similar/comparable lens powers.
- b. The contact lenses will be provided to participants in a manner that does not unmask the participant as described in Section 5.2.4.
- c. The participant will insert the lenses.
- d. [REDACTED]
[REDACTED]
- e. [REDACTED]
[REDACTED]
[REDACTED]

5.3.3 DISPENSING LENS TYPE #1 (VISIT 2)

The procedures to be performed are outlined below:

1. The participant will be assigned a randomization ID (by the research assistant) and the first pair (lens pair #1) of contact lenses (either test or control lens) will be selected according to the randomization table.
2. Lens pair #1 will be provided to participants in a manner which does not unmask the participant or investigator, as described in Section 5.2.4.
3. The participant will insert the lenses.
4. The contact lenses will be allowed to settle for 10 minutes.
5. The participant will be asked to give subjective binocular ratings for:
 - a. [REDACTED]
6. [REDACTED]
7. [REDACTED]
8. Lens [REDACTED] fit will be assessed and graded according to the following grading scales:
 - a. [REDACTED]
 - b. [REDACTED]
 - c. Lens push-up tightness in primary gaze (0 – 100 scale);
 - d. Centration in primary gaze (scale: optimal, slight decentration, moderate decentration but not encroaching limbus, excessive & occasionally encroaching limbus);
 - e. Post-blink movement in primary gaze (mm);
 - f. Overall fit acceptance (0 – 4 scale, and reason if Grade 2 or less).
9. [REDACTED]

- b) [REDACTED]
 - c) Lens push-up tightness in primary gaze (0 – 100 scale);
 - d) Centration in primary gaze (scale: optimal, slight decentration, moderate decentration but not encroaching limbus, excessive & occasionally encroaching limbus);
 - e) Post-blink movement in primary gaze (mm);
 - f) Overall fit acceptance (0 – 4 scale and reason if Grade 2 or less).
6. Study lens collection at 1-week: investigator will remove study lenses from participant eyes while wearing a pair of disposable non-latex medical grade gloves. The lenses will be rinsed and stored according to sponsor instructions which will be provided at a later date. They will be labeled with study name, participant study ID, eye, visit# and date without any identifying characteristics. They will be stored in a -80 degrees centigrade freezer and shipped to the sponsor when all participants have completed the study.
 7. Slit lamp biomicroscopy assessments (see 5.3.2 for details).
 8. There will be a washout of 10 minutes after lens removal if Visit 4 is to be concurrent with this visit.

5.3.5 DISPENSING LENS TYPE #2 (VISIT 4)

1. The participant will be assigned the second pair (lens pair #2) of contact lenses (either test or control lens), which will be selected according to the randomization table.
2. Lens pair #2 will be provided to participants in a manner, which does not unmask the participant or investigator, as described in Section 5.2.4.
3. The participant will insert the lenses.
4. The contact lenses will be allowed to settle for 10 minutes.
5. The same procedures will be followed as described in Section 5.3.3 DISPENSING LENS PAIR #1 (VISIT 2), points 5 to 11. [REDACTED]
6. The participant will be reminded to return for Visit 5 (1-week follow-up visit of study lens #2) and instructed to return used lens foils plus all leftover unworn lenses.

5.3.6 1-WEEK FOLLOW-UP OF LENS TYPE #2 (VISIT 5)

Participants will be asked to wear lenses for 6-8 hours prior to the visit. Participants who attend without wearing lenses for 6-8 hours will be rescheduled (unless they report problems when wearing the lenses).

1. The same procedures will be carried out as described in Section 5.3.4 1-WEEK FOLLOW-UP OF LENS TYPE #1 (VISIT 3), points 1 to 5.
2. Study lens collection at 1-week: investigator will remove study lenses from participant eyes while wearing a pair of disposable non-latex medical grade gloves. The lenses will be rinsed and stored according to sponsor instructions which will be provided at a later date. They will be labeled with study name, participant study ID, eye, visit# and date without any identifying characteristics. They will be stored in a -80 degrees centigrade freezer and shipped to the sponsor when all participants have completed the study.
3. [REDACTED]
4. [REDACTED]
[REDACTED]
[REDACTED]
[REDACTED]
5. [REDACTED]
 - [REDACTED]
 - [REDACTED]
 - [REDACTED]
 - [REDACTED]
 - [REDACTED]
 - [REDACTED]
 - [REDACTED]
 - [REDACTED]
 - [REDACTED]
 - [REDACTED]
 - [REDACTED]

5.3.7 STUDY EXIT

The study exit form will be completed when a participant exits the study. This form will be completed either at study completion, or if the participant is discontinued from the study at another time. A study exit form must be completed for all participants who have taken a study ID number. If in the opinion of the investigator post-study follow-up visits are required, the exit form will be completed after the last follow-up visit.

[REDACTED]

After the exit assessments have been completed, the participant and investigator will complete the study completion and remuneration forms. At this time the participant will be considered as having exited the study.

5.3.8 UNSCHEDULED VISITS

An unscheduled visit is defined as an interim visit requested by the participant or investigator due to an unanticipated problem. Data recorded at these visits will be entered into the database. Only relevant and applicable unscheduled visit information will be included in the final report as deemed necessary by the lead investigator.

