4.1.3 RANDOMIZATION

A randomization schedule will be generated using a web-based program: (for example www.randomization.com) by CORE's Data management team, and provided to the research assistants for the study. The schedule will determine the order of lens wear for participants in the study. Study investigators will remain masked to the randomization schedule until the study is completed and the database has been locked.

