4.1.4 MASKING

Participants will be masked to the lens assignment. Lenses dispensed to participants may be either over-labelled or have part of the label obscured, however the safety information shall be clearly visible. Investigators will be masked as much as possible however it may not be possible to fully mask the investigators, because identifying lens markings may be visible during the biomicroscopy examination.

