8 ADVERSE EVENTS

See CORE SOP012_v02 for a description of all adverse events, including management and reporting. An 'adverse event' refers to any undesirable clinical occurrence in a participant, whether

it is considered to be device-related or not. Adverse events (AE) may be classified as ‘unanticipated adverse device effects,’ ‘serious adverse events,’ ‘significant adverse events,’ or ‘non-significant adverse events,’ as defined below, Table 4.

A number of conditions may result in temporary suspension until resolution. These include corneal infiltrates, corneal staining, limbal injection, bulbar injection or tarsal conjunctival abnormalities.

Table 4: Classification of types of adverse event

Classification	Definition
Serious Adverse Event	Those events that are life-threatening, or result in permanent impairment of a body function, or permanent damage to a body structure or necessitate medical (therapeutic) or surgical intervention to preclude permanent impairment of a body function or permanent damage to a body structure.
Significant Adverse Event	Those non-serious adverse events that occur with contact lens usage that are not sight-threatening but are usually symptomatic and may warrant therapeutic management and /or temporary or permanent discontinuation of contact lens wear.
Non-Significant Adverse Events	Those less severe non-serious adverse events that occur with contact lens usage that are not sight-threatening, may or may not be symptomatic and may warrant palliative management, such as ocular lubricants or temporary interruption of contact lens wear.
Unanticipated Adverse Device Effect	Adverse events in a study that were not previously identified in the protocol in terms of nature, severity, or degree of incidence. An Unanticipated Serious Adverse Device Effect is an unanticipated adverse event that is serious in nature and caused by or associated with the device and is considered reportable.

AE classification, coding (for reporting to the sponsor) and reporting details, plus examples, are provided in Table 5.

Table 5: Contact lens adverse event classification, coding and reporting guide

Code	Condition	Reporting
Serious Adverse Events		
01	Presumed infectious keratitis or infectious corneal ulcer	For all serious AEs: Notify sponsor as soon as possible, within 24 hours;
02	Permanent loss of ≥ 2 lines of best spectacle corrected visual acuity (BSCVA)	
03	Corneal injury that results in permanent opacification within central cornea (6mm)	

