8.1 NORMAL OR ADAPTIVE SYMPTOMS

Transient symptoms such as end-of-day dryness, lens awareness, itching or burning or other discomfort may occur with contact lens wear and may occasionally reduce wearing time. These are

not reported as adverse events unless in the investigator's opinion they are unexpected in nature, severe or have a high rate of occurrence.

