12 STATISTICAL ANALYSIS AND DATA MANAGEMENT

12.1 STATISTICAL ANALYSIS

Primary comparisons will be between study lenses, however there are some variables collected over time with the same lens and this time comparison will be analysed (e.g. 'at-home ratings on Days 1, 3 and 5).

All data will be analyzed by CORE at the University of Waterloo. Unmasked data analysis will be conducted using Statistica, SPSS, or other appropriate software. Descriptive statistics will be provided on information regarding baseline variables (age, gender, refractive error distribution, etc.). Table 6 lists the main outcome variables and anticipated statistical procedures. All data will be tested for normality of distribution using Shapiro-Wilk tests.

[figure not shown]

Table 6: Statistical analysis to be conducted

Variable	Analysis	Statistical test
Subjective ratings	Descriptive and other statistics	Mean, Median*, Standard Deviation, Minimum, Maximum, Frequency count
	Effect of treatment on outcome variable within subjects (comparison between study days) Effect of time on ratings (comparison over time)	Friedman Wilcoxon matched pairs test
[REDACTED]	Descriptive statistics	Mean, Median*, Standard Deviation, Minimum, Maximum, Count
	Effect of treatment on outcome variable within subjects (comparison between study days)	RMANOVA Paired t-test

* For non-parametric data only

The critical alpha level for statistical significance will be set at 0.05, with no adjustments for multiple comparisons.

All participants who were evaluated will be included in the analysis, unless their removal is agreed by the sponsor due to protocol deviations and/or adverse events. In the event of missing data, individual data points will not be extrapolated from the collected data.

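### Unscheduled visits are all recorded but reach the final report at the lead investigator's discretion, with no criteria, no count by lens and no requirement to choose before unmasking (minor)

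*Combined protocol and SAP*

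**What the plan says.** Section 5.3.8 makes three statements. The first ties the visit to a problem: "An unscheduled visit is defined as an interim visit requested by the participant or investigator due to an unanticipated problem". The second secures the data: "Data recorded at these visits will be entered into the database". The third governs what a reader will see: "Only relevant and applicable unscheduled visit information will be included in the final report as deemed necessary by the lead investigator".

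Section 8 is broad on adverse events: the term "refers to any undesirable clinical occurrence in a participant", whether or not the device caused it. Section 8.1 then sets aside transient symptoms such as dryness, lens awareness and burning, even where they shorten wearing time, unless the investigator thinks that "they are unexpected in nature, severe or have a high rate of occurrence".

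On masking, Section 4.1.3 says: "Study investigators will remain masked to the randomization schedule until the study is completed and the database has been locked". Section 4.1.4 concedes that "it may not be possible to fully mask the investigators", because lens markings can show at the slit lamp. Section 12.1 adds: "Unmasked data analysis will be conducted using Statistica, SPSS, or other appropriate software".

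Elsewhere the reporting rules are unconditional. All adverse events (Section 8.3), all discontinuations with their reasons (Section 9) and all protocol deviations (Section 15.4.3) go into the report.

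**The concern.** The protocol promises complete reporting of three kinds of event, yet applies a discretionary filter to visits that exist only because something went wrong. The filter has no stated criteria and no required count by lens. In a two-lens crossover, the reader wants to know whether one lens sent people back to the clinic more often than the other. If the choice of which visits to mention is made by someone who knows or can guess the lens, the reported contrast can reflect the choice as well as the lenses. The reader of the report could not tell, since omitted visits leave no trace there. At stake is the completeness of tolerability reporting, not the fit comparison.

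**Working it through.** The plan gives no figure on this point to reproduce, so the check is mainly a comparison of rules.

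**Step 1. Follow one case.** Suppose a participant returns mid-week because a lens burns, is reassured, and continues on schedule. These are the ways the event could reach the report:

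| Route | Rule | Does it guarantee that the event appears? |
|---|---|---|
| Adverse event | Section 8.3: all are reported | Only if coded as one. Section 8.1 leaves transient discomfort to the investigator's opinion. In Table 5, code 20 needs a judgement that the symptom warrants classification, and code 24 needs a recommended break in wear of more than 1 day. |
| Discontinuation | Section 9: all, with reasons | No, because the participant continues. |
| Protocol deviation | Section 15.4.3: all | No, because the schedule is kept. |
| Defective lens | Section 10: reported to the sponsor | Not stated for the final report. |
| Problem review at Visits 3 and 5 | Table 3 | Collected, but the visible text promises no table of it. Free-text comments fall under a similar discretion (Section 12.3). |
| Rewetting-drop use, wear schedule, subjective ratings | Section 5.2.2, Tables 3 and 6 | May reflect the discomfort indirectly, but need not show that the participant came back. |
| Unscheduled visit | Section 5.3.8 | No, it is discretionary. |

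For this case, the two direct routes (adverse event coding and inclusion of the visit) both rest on investigator judgement. The same holds for a vision or handling complaint that is not coded as an adverse event. A lens replaced at an unscheduled visit (Table 3 footnote) also has no assured place in the report.

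**Step 2. Timing and masking.** Section 4.1.3 ends investigator masking at study completion and database lock. Section 12.1 makes the analysis unmasked. Neither says when, or in what masking state, the relevance of an unscheduled visit is judged. The supportable statement is that nothing requires the judgement to come before unmasking. An earlier judgement would help but would not be fully protected, given the limit conceded in Section 4.1.4.

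**Step 3. Size.** A bias estimate needs the number of unscheduled visits per lens and the share omitted. The documents give neither. All that can be given is the granularity of a count by lens, from the numbers in Section 5.1.1 (38 dispensed, 34 completing):

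- 1/38 = 2.6%
- 1/34 = 2.9%

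Leaving out one participant's only unscheduled visit would move that lens's proportion by about 2.6 to 2.9 percentage points. This describes the denominator and is not an estimate of what will happen.

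**Step 4. What is not touched.** The primary outcome (overall fit acceptance at one week) and the secondary outcomes (centration, post-blink movement, push-up tightness) are measured at scheduled visits (Section 2). Neither they nor the sample size depend on Section 5.3.8.

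**The case against.** The strongest reply is that little can slip through. Adverse events are broadly defined and all reported, as are discontinuations (with symptoms and unacceptable comfort or vision among the listed reasons) and deviations. A symptom that prompts a visit for an unanticipated problem is already a candidate for the exception in Section 8.1. Every unscheduled visit is in the database, the sponsor can ask for a copy (Section 12.2), and the person choosing is the lead investigator, not the sponsor. Some visits will only replace dropped or misplaced lenses. Part of Section 8.3 is redacted, and adverse event handling is also covered by an SOP outside the public text. The study is minimal risk, with approved lenses worn for about a week each.

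Most of this stands, and it narrows the point to problems that are not adverse events, discontinuations or deviations. It does not remove the point, because the exception in Section 8.1 is itself a matter of opinion, and a complete database does not help someone who has only the report.

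Three stronger readings are tempting, and the documents support none of them:

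- A reader might infer that the choice is made after unmasking, with the lens known. A final report usually follows database lock, but no section dates the decision.
- A reader might infer that these visits are the only tolerability signal between scheduled visits apart from the ratings. Rewetting-drop use is tracked (Section 5.2.2), and Table 3 includes a problem review at Visits 3 and 5 and the wear schedule.
- A reader might construct a contrast from equal visit numbers on the two lenses with some of one lens's visits dropped. Any such example rests on an invented rate and says nothing about this trial.

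**Conclusion.** The point holds as a minor one. Section 5.3.8 sets an affirmative rule of discretionary reporting for problem-driven visits, without criteria, without a count by lens, and without a requirement to decide before unmasking. It affects how completely tolerability problems are reported. It does not affect the data held or the fit outcomes. The size of any distortion is unknown and cannot be derived from the documents. The conclusion assumes that the redacted text and the SOP do not already require a full listing. If they do, Section 5.3.8 needs only to be brought into line with them.

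**What to change.** Replace the last sentence of Section 5.3.8 with:

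> All unscheduled visits will be listed in the final report with lens worn, period, day of wear, reason, findings and outcome, and the number of participants with at least one will be shown by lens.

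The discretion in Section 12.3 over free-text comments can stay. The cost is one listing and one small count table. The data are already to be entered in the database; I assume that the visit record includes the reason and findings, and the lens and period follow from the visit date and the randomization schedule. The downside is a slightly longer report that includes trivial visits, such as those for dropped or misplaced lenses, which the reason column identifies. No visit, measurement or clinical rule changes.
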